Ultrasound. Doppler ultrasound assesses foetal behaviour with ultrasonic sound which is emitted by a probe and reflected by tissues while it travels through the amniotic fluid surrounding the foetus. Tissue reflections are then received by a probe and transformed in either a two-, three- or four-dimensional image (Reid & Dunn, 2021). Ultrasound allows direct assessment of foetal behaviour either to explore specific foetal behaviours (observational studies) or to investigate causal relationships between external stimulation and foetal responses (experimental studies). One of the drawbacks of this method is its high attrition rate (> 50 %) as the orientation of the foetus cannot be determined or changed in advance as well as the method itself restricts external stimulation. Nevertheless, the high resolution of ultrasound enables the assessment of foetal behaviour, which is a key strength of this method and one of the reasons why it has been used extensively for intrauterine perception studies (Reid & Dunn, 2021). All studies of this PhD will therefore use two-dimensional ultrasound (2D-ultrasound) in a transverse probe orientation to determine foetal behavioural state and to

ensure the correct positioning of the cardiotocograph in studies 1a and 1b and of the fNIRS probe in studies 2a and 2b.

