As there have not been any previous studies investigating the perception and discrimination of musical timbres and chords in the foetus, there were no previous effect sizes for the estimation of sample size. Therefore, to maximize the probability to find an effect, a conservative, small within factor effect of $f = .1$ was chosen. Based on a probability of $1 - \beta = .95$, an α -value of $\alpha = .05$ and a theoretical correlation of $\rho = .50$ between repeated measurements, a priori calculation using G.Power 3.1.3 (Faul et al., 2009) yielded in a sample size of $N = 84$ for 18 trials per condition for the HR timbre experiment (study 1a). Using the same psychometric input values ($f = .1$, $1 - \beta = .95$, $\alpha = .05$, and $\rho = .50$), a sample size of $N = 60$ was calculated for the HR chord experiment (study 2b) which includes 30 trials per chord category (major vs. minor). Given an attrition rate of approximately 20 % in foetal HR studies (e. g. Lecanuet et al., 1992; Lecanuet et al., 2000) data of 101 participants will be collected for the HR studies.

Using the same psychometric input values ($f = .1$, $\alpha = .05$, $1 - \beta = .95$, and $\rho = .50$), a sample size of $N = 69$ for 24 trials per timbre and $N = 70$ for 24 trials per chord category was calculated for the studies 2a and 2b, respectively. Previous fNIRS studies with newborns reported an

attrition of approximately 40 % (for review, see Lloyd-Fox et al., 2010) while foetal neuroimaging studies sometimes had to exclude 50 % of their participants (e. g. Jardri et al., 2008). Because no one has used fNIRS for foetal research before, sample size estimation will be based on a conservative attrition rate of 50 % and 105 women will be collected for the fNIRS studies.

Please note that the final estimated sample size for both set of studies was oriented on the estimations for the experiment where a larger number of participants was needed to find a small effect of $f = .1$. This was the timbre experiment for the HR studies and the chord experiment for the fNIRS studies.

15. Māori consultation

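### Section 14 inflates for attrition with N × (1 + d) instead of N / (1 − d), so 105 fNIRS women leave about 52 analysable foetuses, not the required 70

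*Protocol*

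**What the plan says.** All the inputs stand in the protocol, section 14 (Estimation of sample size).

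- **fNIRS studies.** The required numbers are 69 for timbre (2a) and 70 for chord (2b); the larger one sets the target. Two attrition rates are cited: about 40 % from newborn fNIRS work, and 50 % from foetal imaging, where "foetal neuroimaging studies sometimes had to exclude 50 % of their participants". The section adopts the higher rate: "sample size estimation will be based on a conservative attrition rate of 50 % and 105 women will be collected for the fNIRS studies".
- **HR studies.** The required numbers are 84 for timbre and 60 for chord; again the larger one sets the target. Attrition is taken as approximately 20 %, and "data of 101 participants will be collected for the HR studies".
- **Power inputs.** All four calculations use f = .1, α = .05, power .95 and a correlation of .50 between repeated measurements.

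The protocol gives no other basis for 105 or 101.

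**The concern.** Each recruitment target is the required number plus d per cent of the required number. Attrition does not work on that base. The section describes it as the share of participants who have to be excluded, so it is taken from the number recruited. Adding 50 % and then losing 50 % leaves three quarters of what was needed.

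At stake is whether the fNIRS studies have the power that the protocol claims for them. This would be the first use of the method in the foetus. A null result in 2a or 2b would be read as coming from a study with a 5 % type II error, when by the protocol's own inputs the analysable sample is about a quarter too small.

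**Working it through.** **1. Reproduce the stated targets.** With required number N and attrition d:

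| Studies | N | d | N × (1 + d) | N / (1 − d) | Stated |
|---|---|---|---|---|---|
| fNIRS | 70 | 0.50 | 70 × 1.5 = 105 | 70 / 0.5 = 140 | 105 |
| HR | 84 | 0.20 | 84 × 1.2 = 100.8, up to 101 | 84 / 0.8 = 105 | 101 |

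Both stated targets match the first formula and neither matches the second. Two matches out of two point to the formula, not to a typing or rounding slip.

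**2. Expected analysable numbers.**

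- fNIRS at 50 %: 105 × 0.5 = 52.5, against 70. The shortfall is 17.5, or 25 %.
- fNIRS at 40 %: 105 × 0.6 = 63, still below 69 and 70.
- Attrition at which 105 yields 70: 1 − 70/105 = 33.3 %, below both rates that section 14 cites.
- HR at 20 %: 101 × 0.8 = 80.8, against 84 for timbre. The 60 needed for chord is exceeded.

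**3. Chance of reaching the required number** (binomial, independent losses at the stated rate).

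- fNIRS: P(70 or more of 105) is 0.0004 at 50 % attrition and about 10 % at 40 %.
- HR: P(84 or more of 101) is about 26 % at 20 % attrition.

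**4. Reproduce the plan's required numbers.** They come back from the noncentral F test for a within factor, with λ = f² × N × m / (1 − ρ), df1 = m − 1 and df2 = (N − k)(m − 1), if m is the number of trials and k the number of stimulus conditions entered as groups:

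- m = 18, k = 3: 82, rounded up to 84 as a multiple of 3 (1a).
- m = 30, k = 2: 60 (HR chord).
- m = 24, k = 3: 69 (2a).
- m = 24, k = 2: 69, rounded up to 70 as an even number (2b).

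**5. Power in that same set-up at the expected yield.**

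- 2b at N = 70: λ = 0.01 × 70 × 24 / 0.5 = 33.6, df 23 and 1564, power .957. At N = 52: λ = 0.01 × 52 × 24 / 0.5 = 24.96, df 23 and 1150, power .853.
- 2a: power .953 at N = 69 and .852 at N = 52.
- Both fNIRS studies at N = 63 (40 % attrition): power .928.
- 1a: power .957 at N = 84, .948 at N = 81 and .945 at N = 80.

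**6. Limit of these power figures.** Section 7 plans a one-way repeated-measures ANOVA over three timbres or two chord categories. If f = .1 and ρ = .50 are applied to those condition means (m = 3 or 2, one group), power at N = 70 is about .43 for 2a and .38 for 2b, and at N = 52 about .32 and .29. So .95 and .85 describe the G*Power set-up, not that test. The shortfall in step 2 does not depend on any power model.

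**The case against.** Several points stand on the other side.

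- **HR.** A reader might infer that both study sets are seriously undersized. They are not. In the plan's set-up .95 is reached at 82, and 84 is that figure rounded up, so an expected 80.8 is about one foetus short on a rate given only as approximate. This half is a correction for consistency.
- **Actual attrition may be lower.** Section 5 lets a woman walk or drink water to prompt repositioning, and come back some days later if the head stays out of range. That could bring losses below 50 %. The 0.0004 is therefore a check of the plan against its own planning rate, not a forecast. It does not rescue the target, because section 14 plans on 50 % and its result must follow from that input. Even at 40 % the expected yield is 63.
- **The word conservative.** A reader might infer from section 4, which puts attrition with ultrasound above 50 %, that 50 % is too low to be called conservative. The protocol does not support this. That rate concerns ultrasound as a way of assessing foetal behaviour, partly because the method restricts stimulation. Here ultrasound establishes behavioural state and guides placement. In section 14, 50 % is the higher of the two rates cited, so the word is fair.
- **What 140 would buy.** A reader might infer that 140 women secure 95 % power for the planned ANOVA. That is not shown; 140 only restores the required 70 in expectation.
- **Feasibility.** The first fNIRS aim is to show that measurement is possible at all, and this power calculation does not govern that aim. The discrimination aims still rest on it.

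**Conclusion.** Section 14 is wrong as written. The inflation formula is incorrect, and no reading of attrition within the section makes 105 consistent with 70 at 50 %.

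The size is material for fNIRS: about 52 expected against 70, a 25 % shortfall. In the plan's own set-up the type II error is about 15 % instead of 5 %, so the stated 95 % power is not delivered for 2a and 2b. For HR it is minor: about 81 against 84, with power within about half a percentage point of .95.

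The yields rest only on the protocol's own required numbers and attrition rates. The power figures rest in addition on its G*Power set-up, with trials as measurements and conditions as groups, and should not be carried over to the analysis in section 7.

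**What to change.** Correct the formula in section 14 to N / (1 − d), then take one of two routes:

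- **Keep 105 and 101.** State the expected analysable numbers, about 52 for fNIRS and 81 for HR, and give the lower power: about .85 for 2a and 2b, and .945 to .948 for 1a.
- **Keep the required numbers.** State the targets that follow from the plan's own inputs: 140 for fNIRS (35 more women) and 105 for HR (4 more).

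On either route, label the power as belonging to the G*Power set-up, and say that it does not describe the repeated-measures ANOVA over two or three conditions.

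The cost is one rewritten paragraph. The first route adds no participants but states a less favourable power; the second adds recruitment. No procedure or clinical rule changes.
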